17.1.8 Safety Outcomes

Table 61: Summary of Adverse Events by Treatment Arm

	Treatment Arm		Total (N=XX)
	Sham (N=XX)	rTMS (N=XX)	
Number of participants with at least one adverse event (AE) ¹	N (X.X%)		
Maximum severity of AE for participants with at least one AE ²			
Grade 1 – Mild	N (X.X%)		
Grade 2 – Moderate			
Grade 3 - Severe			
Number of AEs	N		
Severity of AEs ³			
Grade 1 – Mild	N (X.X%)		
Grade 2 – Moderate			
Grade 3 – Severe			

¹ The percentage is calculated based on the denominator of the number of randomized participants.

² The percentage is calculated with the denominator as the number of participants with AEs.

³ The percentage is calculated with the denominator as the number of AEs.

Table 62: Summary of MedDRA-coded Adverse Events by Treatment Arm

System Organ Class/Preferred Term (MedDRA V26.1)	Treatment Arm		Total (N=XX)
	Sham (N=XX)	rTMS (N=XX)	
Participants with at least one adverse event (AE)	N (X.X%)		
Psychiatric disorders	N (X.X%)		
Suicidal ideation	N (X.X%)		
Suicide attempt			
Self injurious behavior			
Psychotic disorder			
Depression suicidal			
Depression			
Delirium			
Anxiety			
Affective disorder			
Injury, poisoning and procedural complications	N (X.X%)		
Overdose	N (X.X%)		
Multiple fractures			
Burns third degree			
Infections and infestations	N (X.X%)		
Cellulitis	N (X.X%)		
Abscess limb			
Pneumonia			
Influenza			
Nervous system disorders	N (X.X%)		
Syncope	N (X.X%)		
Seizure			
Facial paresis			
Respiratory, thoracic and mediastinal disorders	N (X.X%)		
Respiratory depression	N (X.X%)		
Asthma			
Musculoskeletal and connective tissue disorders	N (X.X%)		
Back pain	N (X.X%)		
Metabolism and nutrition disorders	N (X.X%)		
Dehydration	N (X.X%)		

Percentages are calculated based on the number of participants experiencing the adverse event at least once as the numerator and the number of participants randomized as the denominator.

Example SOC and PT provided.

Listing 1: Adverse Events by Treatment Arm

Treatment Arm = Sham

											MedDRA V26.1	
Site	Participant ID	Date of Randomization	Onset Date	AE Description	Severity of AE	Alternative Etiology	Outcome	Date of Resolution/ Medically Stable	SAE Associated With	Preferred Term	System Organ Class	
xxxxx	xxxxxxxxxxxxxx	mm/dd/yyyy	mm/dd/yyyy	xxxxxxxxxx	Grade 1 – Mild Grade 2 – Moderate Grade 3 – Severe	None apparent Study disease Concomitant medication Other pre-existing disease or condition Accident, trauma, or external factors Concurrent illness/condition (not pre-existing) Study procedures Other	Recovering/ resolving Recovered/ resolved Recovering/ resolved with sequelae Not recovered/ not resolved Fatal Unknown	mm/dd/yyyy	Congenital anomaly or birth defect Persistent or significant disability or incapacity Death Initial or prolonged hospitalization Life threatening Other serious event (Important Medical Event)	xxxxxxx	xxxxxxx	

SAEs are highlighted in grey.

Listing 1: Adverse Events by Treatment Arm											
Treatment Arm = rTMS											MedDRA V26.1
Site	Participant ID	Date of Randomization	Onset Date	AE Description	Severity of AE	Alternative Etiology	Outcome	Date of Resolution/ Medically Stable	SAE Associated With	Preferred Term	System Organ Class
xxxxx	xxxxxxxxxxxxxx	mm/dd/yyyy	mm/dd/yyyy	xxxxxxxxxx	Grade 1 – Mild Grade 2 – Moderate Grade 3 – Severe	None apparent Study disease Concomitant medication Other pre-existing disease or condition Accident, trauma, or external factors Concurrent illness/condition (not pre-existing) Study procedures Other	Recovering/ resolving Recovered/ resolved Recovering/ resolved with sequelae Not recovered/ not resolved Fatal Unknown	mm/dd/yyyy	Congenital anomaly or birth defect Persistent or significant disability or incapacity Death Initial or prolonged hospitalization Life threatening Other serious event (Important Medical Event)	xxxxxxx	xxxxxxxx

Table 63: Summary of Serious Adverse Events by Treatment Arm

	Treatment Arm		Total (N=XX)
	Sham (N=XX)	rTMS (N=XX)	
Number of participants with at least one serious adverse event (SAE) ¹	N (X.X%)		
Number of participants with at least one SAE of the following type ²			
Congenital anomaly or birth defect	N (X.X%)		
Persistent or significant disability or incapacity			
Death			
Initial or prolonged hospitalization			
Life threatening			
Other serious event (Important Medical Event)			
Number of SAEs	N		
Type of SAE ³			
Congenital anomaly or birth defect	N (X.X%)		
Persistent or significant disability or incapacity			
Death			
Initial or prolonged hospitalization			
Life threatening			
Other serious event (Important Medical Event)			

¹ The percentage is calculated based on the denominator of the number of randomized participants.

² The percentage is calculated with the denominator as the number of participants with SAEs.

³ The percentage is calculated with the denominator as the number of SAEs.

Table 64: Summary of MedDRA-coded Serious Adverse Events by Treatment Arm

System Organ Class/Preferred Term (MedDRA V26.1)	Treatment Arm		Total (N=XX)
	Sham (N=XX)	rTMS (N=XX)	
Participants with at least one serious adverse event (SAE)	N (X.X%)		
Psychiatric disorders	N (X.X%)		
Suicidal ideation	N (X.X%)		
Suicide attempt			
Self injurious behavior			
Psychotic disorder			
Depression			
Injury, poisoning and procedural complications	N (X.X%)		
Overdose	N (X.X%)		
Multiple fractures			
Burns third degree			
Infections and infestations	N (X.X%)		
Cellulitis	N (X.X%)		
Abscess limb			
Pneumonia			
Influenza			
Nervous system disorders	N (X.X%)		
Syncope	N (X.X%)		
Seizure			
Facial paresis			
Respiratory, thoracic and mediastinal disorders	N (X.X%)		
Respiratory depression	N (X.X%)		
Asthma			
Musculoskeletal and connective tissue disorders	N (X.X%)		
Back pain	N (X.X%)		
Metabolism and nutrition disorders	N (X.X%)		
Dehydration	N (X.X%)		

Percentages are calculated based on the number of participants experiencing the adverse event at least once as the numerator and the number of participants randomized as the denominator.

Example SOC and PT provided.

Listing 2: Serious Adverse Events by Treatment Arm											
Treatment Arm = Sham										MedDRA V26.1	
Site	Participant ID	Date of Randomization	Onset Date	AE Description	Severity of AE	Alternative Etiology	Outcome	Date of Resolution/ Medically Stable	SAE Associated With	Preferred Term	System Organ Class
xxxxx	xxxxxxxxxxxxxx	mm/dd/yyyy	mm/dd/yyyy	xxxxxxxxx	Grade 1 – Mild Grade 2 – Moderate Grade 3 – Severe	None apparent Study disease Concomitant medication Other pre-existing disease or condition Accident, trauma, or external factors Concurrent illness/condition (not pre-existing) Study procedures Other	Recovering/ resolving Recovered/ resolved Recovering/ resolved with sequelae Not recovered/ not resolved Fatal Unknown	mm/dd/yyyy	Congenital anomaly or birth defect Persistent or significant disability or incapacity Death Initial or prolonged hospitalization Life threatening Other serious event (Important Medical Event)	xxxxxxx	xxxxxxx

Listing 2: Serious Adverse Events by Treatment Arm

Treatment Arm = rTMS

Site	Participant ID	Date of Randomization	Onset Date	AE Description	Severity of AE	Alternative Etiology	Outcome	Date of Resolution/ Medically Stable	SAE Associated With	MedDRA V26.1	
										Preferred Term	System Organ Class
xxxxx	xxxxxxxxxxxxxx	mm/dd/yyyy	mm/dd/yyyy	xxxxxxxxxx	Grade 1 – Mild Grade 2 – Moderate Grade 3 – Severe	None apparent Study disease Concomitant medication Other pre-existing disease or condition Accident, trauma, or external factors Concurrent illness/condition (not pre-existing) Study procedures Other	Recovering/ resolving Recovered/ resolved Recovering/ resolved with sequelae Not recovered/ not resolved Fatal Unknown	mm/dd/yyyy	Congenital anomaly or birth defect Persistent or significant disability or incapacity Death Initial or prolonged hospitalization Life threatening Other serious event (Important Medical Event)	xxxxxxx	xxxxxxxx

Table 65: Summary of Adverse Device Reactions by Treatment Arm

	Treatment Arm		Total (N=XX)
	Sham (N=XX)	rTMS (N=XX)	
Number of participants with at least one adverse device reaction (ADR) ¹	N (X.X%)		
Maximum severity of ADE for participants with at least one ADR ²			
Grade 1 – Mild	N (X.X%)		
Grade 2 – Moderate			
Grade 3 – Severe			
Number of ADEs	N		
Severity of ADEs ³			
Grade 1 – Mild	N (X.X%)		
Grade 2 – Moderate			
Grade 3 – Severe			

¹An adverse device reaction is any adverse event caused by the study device. The percentage is calculated based on the denominator of the number of randomized participants.

²The percentage is calculated with the denominator as the number of participants with ADRs.

³The percentage is calculated with the denominator as the number of ADRs.

Table 66: Summary of MedDRA-coded Adverse Device Reactions by Treatment Arm

System Organ Class/Preferred Term (MedDRA V26.1)	Treatment Arm		Total (N=XX)
	Sham (N=XX)	rTMS (N=XX)	
Participants with at least one adverse device reaction	N (X.X%)		
General disorders and administration site conditions	N (X.X%)		
Medical device site pain	N (X.X%)		
Medical device site discomfort			
Application site discomfort			
Medical device site paraesthesia			
Application site pain			
Chills			
Nervous system disorders	N (X.X%)		
Headache	N (X.X%)		
Paraesthesia			
Head discomfort			

Percentages are calculated based on the number of participants experiencing the adverse event at least once as the numerator and the number of participants randomized as the denominator.

Example SOC and PT provided.

Listing 3: Adverse Device Reactions by Treatment Arm											
Treatment Arm = Sham											MedDRA V26.1
Site	Participant ID	Date of Randomization	Onset Date	AE Description	Severity of AE	Action Taken with the Study Device	Outcome	Date of Resolution/Medically Stable	SAE Associated With	Preferred Term	System Organ Class
xxxxx	xxxxxxxxxxxx	mm/dd/yyyy	mm/dd/yyyy	xxxxxxxx	Grade 1 – Mild Grade 2 – Moderate Grade 3 – Severe	None Decreased rTMS/sham "dose" Temporarily stopped rTMS/sham Permanently stopped rTMS/sham	Recovering/ resolving Recovered/ resolved Recovering/ resolved with sequelae Not recovered/ not resolved Fatal Unknown	mm/dd/yyyy	Congenital anomaly or birth defect Persistent or significant disability or incapacity Death Initial or prolonged hospitalization Life threatening Other serious event (Important Medical Event)	xxxxxxxx	xxxxxxxx

SAEs are highlighted in grey.

Listing 3: Adverse Device Reactions by Treatment Arm											
Treatment Arm = rTMS											
Site	Participant ID	Date of Randomization	Onset Date	AE Description	Severity of AE	Action Taken with the Study Device	Outcome	Date of Resolution/Medically Stable	SAE Associated With	MedDRA V26.1	
xxxxx	xxxxxxxxxxxx	mm/dd/yyyy	mm/dd/yyyy	xxxxxxxxxx	Grade 1 – Mild Grade 2 – Moderate Grade 3 – Severe	None/ Decreased rTMS/sham "dose" Temporarily stopped rTMS/sham Permanently stopped rTMS/sham	Recovering/ resolving Recovered/ resolved Recovering/ resolved with sequelae Not recovered/ not resolved Fatal Unknown	mm/dd/yyyy	Congenital anomaly or birth defect Persistent or significant disability or incapacity Death Initial or prolonged hospitalization Life threatening Other serious event (Important Medical Event)	xxxxxxxx	xxxxxxxx

SAEs are highlighted in grey.

Table 67: Summary of Unanticipated Adverse Device Effects by Treatment Arm

	Treatment Arm		Total (N=XX)
	Sham (N=XX)	rTMS (N=XX)	
Number of participants with at least one unanticipated adverse device effect (UADE) ¹	N (X.X%)		
Number of participants with at least one UADE of the following type ²			
Congenital anomaly or birth defect	N (X.X%)		
Persistent or significant disability or incapacity			
Death			
Initial or prolonged hospitalization			
Life threatening			
Other event (Important Medical Event)			
Number of UADEs	N		
Type of UADE ³			
Congenital anomaly or birth defect	N (X.X%)		
Persistent or significant disability or incapacity			
Death			
Initial or prolonged hospitalization			
Life threatening			
Other event (Important Medical Event)			

¹ The percentage is calculated based on the denominator of the number of randomized participants.

² The percentage is calculated with the denominator as the number of participants with UADEs.

³ The percentage is calculated with the denominator as the number of UADEs.

Table 68: Summary of MedDRA-coded Unanticipated Adverse Device Effects by Treatment Arm

System Organ Class/Preferred Term (MedDRA V26.1)	Treatment Arm		Total (N=XX)
	Sham (N=XX)	rTMS (N=XX)	
Participants with at least one unanticipated adverse device effect	N (X.X%)		
General disorders and administration site conditions	N (X.X%)		
Medical device site pain	N (X.X%)		
Medical device site discomfort			
Application site discomfort			
Medical device site paraesthesia			
Application site pain			

Percentages are calculated based on the number of participants experiencing the adverse event at least once as the numerator and the number of participants randomized as the denominator.

Example SOC and PT provided.

Listing 4: Unanticipated Adverse Device Effects by Treatment Arm										
Treatment Arm = Sham										
Site	Participant ID	Date of Randomization	Onset Date	AE Description	Severity of AE	Action Taken with the Study Device	Outcome	Date of Resolution/Medically Stable	SAE Associated With	MedDRA V26.1
xxxxx	xxxxxxxxxxxx	mm/dd/yyyy	mm/dd/yyyy	xxxxxxxx	Grade 1 – Mild Grade 2 – Moderate Grade 3 – Severe	None Decreased rTMS/sham "dose" Temporarily stopped rTMS/sham Permanently stopped rTMS/sham	Recovering/ resolving Recovered/ resolved Recovering/ resolved with sequelae Not recovered/ not resolved Fatal Unknown	mm/dd/yyyy	Congenital anomaly or birth defect Persistent or significant disability or incapacity Death Initial or prolonged hospitalization Life threatening Other serious event (Important Medical Event)	xxxxxxxx xxxxxxxx

SAEs are highlighted in grey.

Listing 4: Unanticipated Adverse Device Effects by Treatment Arm											
Treatment Arm = rTMS											
Site	Participant ID	Date of Randomization	Onset Date	AE Description	Severity of AE	Action Taken with the Study Device	Outcome	Date of Resolution/ Medically Stable	SAE Associated With	MedDRA V26.1	
xxxxx	xxxxxxxxxxxxxx	mm/dd/yyyy	mm/dd/yyyy	xxxxxxxxxx	Grade 1 – Mild Grade 2 – Moderate Grade 3 – Severe	None Decreased rTMS/sham "dose" Temporarily stopped rTMS/sham Permanently stopped rTMS/sham	Recovering/ resolving Recovered/ resolved Recovering/ resolved with sequelae Not recovered/ not resolved Fatal Unknown	mm/dd/yyyy	Congenital anomaly or birth defect Persistent or significant disability or incapacity Death Initial or prolonged hospitalization Life threatening Other serious event (Important Medical Event)	xxxxxxxxxx	xxxxxxxxxx

SAEs are highlighted in grey.

Table 69: Summary of CHRT – Participant Rated by Treatment Arm

Major Depressive Episode ¹	Number with suicide ideation/intent on CHRT-SR ^{2,3}	Treatment Arm		Total (N=XX)
		Sham (N=XX)	rTMS (N=XX)	
Absent	During screening	N (X.X%)	N (X.X%)	N (X.X%)
	During treatment period			
	During follow-up period			
Present	During screening			
	During treatment period			
	During follow-up period			
Overall	During screening			
	During treatment period			
	During follow-up period			

¹ Current Major Depressive Episode is assessed via the Mini International Neuropsychiatric Interview at baseline.

² Concise Health Risk Tracking-Participant Rated (CHRT-SR). Suicide ideation/intent on CHRT is defined as a response of "Agree" or "Strongly Agree" on any of CHRT-SR questions 14, 15 or 16: In the past week "I have been having thoughts of killing myself", "I have thoughts about how I might kill myself" or "I have a plan to kill myself".

³ Unique randomized participants with suicidal ideation/intent, at least once during the treatment and/or follow-up period. Denominator is the number randomized.

Listing 5: CHRT¹ Participant Rated by Treatment Arm								
Treatment Arm = Sham								
Site	Participant ID	Date of Randomization	Major Depressive Episode²	Visit	Date of Assessment	I have been having thoughts of killing myself	I have thoughts about how I might kill myself	I have a plan to kill myself
xxxxxxxxxx	xxxxxxxxxxxxxx	mm/dd/yyyy	Absent/ Present	Screening Week 1 A1 Week 1 A2 etc.	mm/dd/yyyy	Strongly Disagree Disagree Neither Agree nor Disagree/ Agree Strongly Agree	Strongly Disagree Disagree Neither Agree nor Disagree Agree Strongly Agree	Strongly Disagree Disagree Neither Agree nor Disagree Agree Strongly Agree

All visits are included for randomized participants who answered, 'Agree' or 'Strongly Agree'. Responses of 'Agree' are highlighted in orange and 'Strongly Agree' are highlighted in red.

¹ Concise Health Risk Tracking – Participant Rated (CHRT-SR) form.

² Current Major Depressive Episode is assessed via the Mini International Neuropsychiatric Interview at baseline.

Listing 5: CHRT¹ Participant Rated by Treatment Arm								
Treatment Arm = rTMS								
Site	Participant ID	Date of Randomization	Major Depressive Episode²	Visit	Date of Assessment	I have been having thoughts of killing myself	I have thoughts about how I might kill myself	I have a plan to kill myself
xxxxxxxxxx	xxxxxxxxxxxxxx	mm/dd/yyyy	Absent/ Present	Screening Week 1 A1 Week 1 A2 etc.	mm/dd/yyyy	Strongly Disagree Disagree Neither Agree nor Disagree/ Agree Strongly Agree	Strongly Disagree Disagree Neither Agree nor Disagree Agree Strongly Agree	Strongly Disagree Disagree Neither Agree nor Disagree Agree Strongly Agree

All visits are included for randomized participants who answered 'Agree' or 'Strongly Agree'. Responses of 'Agree' are highlighted in orange and 'Strongly Agree' are highlighted in red.

¹ Concise Health Risk Tracking – Participant Rated (CHRT-SR) form.

² Current Major Depressive Episode is assessed via the Mini International Neuropsychiatric Interview at baseline.

Table 70: Summary of CHRT – Clinician Rated by Treatment Arm

Major Depressive Episode ¹	Time Period	Suicidal Ideation/Attempt	Treatment Arm		Total (N=XX)
			Sham (N=XX)	rTMS (N=XX)	
Absent	Screening	Number with passive suicide ideation	N (X.X%)	N (X.X%)	N (X.X%)
		Number with active/non-specific suicidal ideation			
		Number with active suicidal ideation with method			
		Number with active suicidal ideation with method and intent			
		Number with active suicidal ideation with method, intent, and plan			
		Number with suicide attempt reported			
	Treatment Period	Number with passive suicide ideation			
		Number with active/non-specific suicidal ideation			
		Number with active suicidal ideation with method			
		Number with active suicidal ideation with method and intent			
		Number with active suicidal ideation with method, intent, and plan			
		Number with suicide attempt reported			
	Follow-up Period	Number with passive suicide ideation			
		Number with active/non-specific suicidal ideation			
		Number with active suicidal ideation with method			
		Number with active suicidal ideation with method and intent			
		Number with active suicidal ideation with method, intent, and plan			
		Number with suicide attempt reported			
Present	Screening	Number with passive suicide ideation			
		Number with active/non-specific suicidal ideation			
		Number with active suicidal ideation with method			
		Number with active suicidal ideation with method and intent			
		Number with active suicidal ideation with method, intent, and plan			
		Number with suicide attempt reported			
	Treatment Period	Number with passive suicide ideation			
		Number with active/non-specific suicidal ideation			
		Number with active suicidal ideation with method			
		Number with active suicidal ideation with method and intent			
		Number with active suicidal ideation with method, intent, and plan			
		Number with suicide attempt reported			
	Follow-up Period	Number with passive suicide ideation			
		Number with active/non-specific suicidal ideation			
		Number with active suicidal ideation with method			
		Number with active suicidal ideation with method and intent			
		Number with active suicidal ideation with method, intent, and plan			
		Number with suicide attempt reported			

Table 70: Summary of CHRT – Clinician Rated by Treatment Arm

Major Depressive Episode ¹	Time Period	Suicidal Ideation/Attempt	Treatment Arm		Total (N=XX)
			Sham (N=XX)	rTMS (N=XX)	
Overall	Screening	Number with passive suicide ideation			
		Number with active/non-specific suicidal ideation			
		Number with active suicidal ideation with method			
		Number with active suicidal ideation with method and intent			
		Number with active suicidal ideation with method, intent, and plan			
		Number with suicide attempt reported			
	Treatment Period	Number with passive suicide ideation			
		Number with active/non-specific suicidal ideation			
		Number with active suicidal ideation with method			
		Number with active suicidal ideation with method and intent			
		Number with active suicidal ideation with method, intent, and plan			
		Number with suicide attempt reported			
	Follow-up Period	Number with passive suicide ideation			
		Number with active/non-specific suicidal ideation			
		Number with active suicidal ideation with method			
		Number with active suicidal ideation with method and intent			
		Number with active suicidal ideation with method, intent, and plan			
		Number with suicide attempt reported			

Concise Health Risk Tracking- Clinician Rated Module (CHRT- CR) will be performed by the Medical Clinician only if a participant endorses any of questions 14 -16 on the CHRT-SR as “Agree” or “Strongly agree”. Percentage within the time period is calculated as the number of unique randomized participants with the specified type of suicidal ideation/attempt at least once during the week prior to the visit where the assessment occurs, divided by the number of participants randomized.

¹ Current Major Depressive Episode is assessed via the Mini International Neuropsychiatric Interview at baseline.

Listing 6: CHRT ¹ Clinician Rated by Treatment Arm											
Treatment Arm = Sham											
Site	Participant ID	Date of Randomization	Major Depressive Episode ²	Visit	Date of Assessment	Suicidal Ideation					
						Passive	Active/ Non-specific	Active with Method	Active with Method and Intent	Active with Method, Intent and Plan	
xxxxxxxxxx	xxxxxxxxxx	mm/dd/yyyy	Absent/ Present	Screening Week 1 A1 Week 1 A2 etc.	mm/dd/yyyy	No/Yes	No/Yes	No/Yes	No/Yes	No/Yes	No/Yes

All visits are included for randomized participants who answered, 'Agree' or 'Strongly Agree' to any of the Concise Health Risk Tracking - Participant Rated (CHRT-SR) questions 14, 15 or 16: In the past week "I have been having thoughts of killing myself", "I have thoughts about how I might kill myself" or "I have a plan to kill myself".

¹ Concise Health Risk Tracking – Clinician Rated Module (CHRT-CR) form.

² Current Major Depressive Episode is assessed via the Mini International Neuropsychiatric Interview at baseline.

Listing 6: CHRT ¹ Clinician Rated by Treatment Arm											
Treatment Arm = rTMS											
Site	Participant ID	Date of Randomization	Major Depressive Episode ²	Visit	Date of Assessment	Suicidal Ideation					
						Passive	Active/ Non-specific	Active with Method	Active with Method and Intent	Active with Method, Intent and Plan	
xxxxxxxxxx	xxxxxxxxxx	mm/dd/yyyy	Absent/ Present	Screening Week 1 A1 Week 1 A2 etc.	mm/dd/yyyy	No/Yes	No/Yes	No/Yes	No/Yes	No/Yes	No/Yes

All visits are included for randomized participants who answered, 'Agree' or 'Strongly Agree' to any of the Concise Health Risk Tracking - Participant Rated (CHRT-SR) questions 14, 15 or 16: In the past week "I have been having thoughts of killing myself", "I have thoughts about how I might kill myself" or "I have a plan to kill myself".

¹ Concise Health Risk Tracking – Clinician Rated Module (CHRT-CR) form.

² Current Major Depressive Episode is assessed via the Mini International Neuropsychiatric Interview at baseline'.

Listing 7: Pregnancies by Treatment Arm							
Treatment = Sham							
Site	Participant ID	Date of Randomization	Date Staff Aware of Pregnancy	Date Pregnancy Confirmed	Date of Pregnancy Outcome	Pregnancy Outcome	Normal Infant?
xxxxx	xxxxxxxxxxxx	mm/dd/yyyy	mm/dd/yyyy	mm/dd/yyyy	mm/dd/yyyy	Vaginal delivery Cesarean delivery Miscarriage Termination Other Unknown	Yes/No

Listing 7: Pregnancies by Treatment Arm							
Treatment = rTMS							
Site	Participant ID	Date of Randomization	Date Staff Aware of Pregnancy	Date Pregnancy Confirmed	Date of Pregnancy Outcome	Pregnancy Outcome	Normal Infant?
xxxxx	xxxxxxxxxxxx	mm/dd/yyyy	mm/dd/yyyy	mm/dd/yyyy	mm/dd/yyyy	Vaginal delivery Cesarean delivery Miscarriage Termination Other Unknown	Yes/No

Listing 8: Deaths by Treatment Arm					
Treatment Arm = Not Randomized					
Site	Participant ID	Date of Death	Description	MedDRA V26.1	
				Preferred Term	System Organ Class
xxxxx	xxxxxxxxxxxx	mm/dd/yyyy	xxxxxxxxxxxxxxxxxxxxxxxxxxxx	xxxxxxxxxxxxxxxxxxxxxxxxxxxx	xxxxxxxxxxxxxxxxxxxxxxxxxxxx

Listing 8: Deaths by Treatment Arm					
Treatment Arm = Sham					
Site	Participant ID	Date of Randomization	Date of Death	Description	MedDRA V26.1
					Preferred Term
xxxxx	xxxxxxxxxxxx	mm/dd/yyyy	mm/dd/yyyy	xxxxxxxxxxxxxxxxxxxxxxxxxxxx	xxxxxxxxxxxxxxxxxxxxxxxxxxxx

Listing 8: Deaths by Treatment Arm					
Treatment Arm = rTMS					
Site	Participant ID	Date of Randomization	Date of Death	Description	MedDRA V26.1
					Preferred Term
xxxxx	xxxxxxxxxxxx	mm/dd/yyyy	mm/dd/yyyy	xxxxxxxxxxxxxxxxxxxxxxxxxxxx	xxxxxxxxxxxxxxxxxxxxxxxxxxxx

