8.1 Adverse Events

Adverse events (AEs) are defined in Sections 3.2.7. The number and proportion of the following measures will be provided by treatment arm and overall: participants with at least one AE,

participants with at least one AE by maximum severity, total number of AEs, and severity of AEs. The number and proportion of participants experiencing the AE at least once will also be summarized by System Organ Class (SOC) and Preferred Term (PT).

A listing will include site, participant ID, date of randomization, event onset date, event description, severity, alternate etiology, outcome, resolution date, SAE associated with (if applicable), and the MedDRA® coded PT and SOC.

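### Participant-level severity and type percentages in SAP safety Tables 61, 63, 65 and 67 are taken among participants who already have an event, so they are not per-arm risks

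*SAP*

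**What the plan says.** SAP Section 8.1 asks for the number and proportion, by arm and overall, of several measures, including "participants with at least one AE by maximum severity, total number of AEs, and severity of AEs". It names no denominator, so the table-shell footnotes in Section 17.1.8 decide what is printed.

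Table 61 uses three bases:
- Participants with any AE (footnote 1): "The percentage is calculated based on the denominator of the number of randomized participants".
- Participants by maximum severity (footnote 2): "The percentage is calculated with the denominator as the number of participants with AEs".
- Events by severity (footnote 3): "The percentage is calculated with the denominator as the number of AEs".

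The other three summary tables follow the same pattern. For SAE type in Table 63, footnote 2 reads "The percentage is calculated with the denominator as the number of participants with SAEs". For UADE type in Table 67 it reads "The percentage is calculated with the denominator as the number of participants with UADEs". Footnote 2 of Table 65 does the same for maximum ADR severity, dividing by participants with an ADR.

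Tables 62, 64, 66 and 68, which break events down by system organ class and preferred term, take "the number of participants randomized as the denominator". They do not split by severity.

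**The concern.** A by-arm percentage in a safety table is naturally read as a risk in that arm. Here the denominator is participants with at least one event, which is itself an outcome that treatment may change. The percentage answers a different question: among those with an event, how many had a severe one, or one of the given type. Two arms with the same risk of a severe event can then show different percentages, and a real difference can look smaller, vanish or change direction.

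This matters most for severity. Protocol Section 4.3.1 says the precise risks of the device in these populations are not yet known. Tables 61 and 65 are the only summary tables that compare participants with Grade 3 events by arm, and neither gives that percentage per participant randomised. The SAE tables do not fill the gap, because severity and seriousness are different classifications.

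**Working it through.** The safety tables are empty shells, so there is no printed figure to reproduce. The check is on the denominator and what follows from it.

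**Inputs.** The plan is to randomise 160 participants (SAP Section 2.2.1) at 1:1 (SAP Section 2.2.4), so 160 / 2 = 80 per treatment arm. The documents give no AE or severe-AE rate by arm. Every event count below is an assumption.

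**Formula.** In one arm let N be the number randomised, a the participants with any AE and s the participants whose worst AE is severe.

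- Printed under footnote 2: s / a
- Risk per randomised participant: s / N
- Link: s / a = (s / N) / (a / N)

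Dividing active by sham gives: ratio of printed percentages = RR(severe) / RR(any AE), with both risk ratios per randomised participant. If RR(severe) is above 1, the printed ratio is
- reversed when RR(any AE) exceeds RR(severe);
- 1, so the difference cancels, when the two are equal;
- shrunk when RR(any AE) lies between 1 and RR(severe);
- undistorted when RR(any AE) is 1;
- exaggerated when RR(any AE) is below 1.

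**Tables 61 and 65, sham vs active, N = 80 each (assumed counts).**

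| Any AE | Severe | Printed s/a | Per randomised s/N | RR severe | RR any AE | Printed ratio |
|---|---|---|---|---|---|---|
| 20 vs 50 | 4 vs 8 | 20.0% vs 16.0% | 5.0% vs 10.0% | 2.00 | 2.50 | 0.80 |
| 30 vs 60 | 4 vs 6 | 13.3% vs 10.0% | 5.0% vs 7.5% | 1.50 | 2.00 | 0.75 |
| 40 vs 60 | 4 vs 6 | 10.0% vs 10.0% | 5.0% vs 7.5% | 1.50 | 1.50 | 1.00 |
| 40 vs 60 | 4 vs 5 | 10.0% vs 8.3% | 5.0% vs 6.25% | 1.25 | 1.50 | 0.83 |
| 40 vs 70 | 4 vs 8 | 10.0% vs 11.4% | 5.0% vs 10.0% | 2.00 | 1.75 | 1.14 |
| 40 vs 40 | 4 vs 6 | 10.0% vs 15.0% | 5.0% vs 7.5% | 1.50 | 1.00 | 1.50 |

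The first, second and fourth rows reverse the difference, the third cancels it, the fifth shrinks it and the sixth leaves the ratio intact. With equal severe risk of 5% per arm and any AE in 50% of sham and 60% of active participants, the table prints 0.05 / 0.50 = 10.0% against 0.05 / 0.60 = 8.3%, a difference where none exists.

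**Tables 63 and 67.** The denominators hold only participants with an SAE or a UADE, so ordinary mild AEs do not enter. Other SAEs or UADEs can still distort the percentage. Assume 2 sham and 6 active participants with any SAE, of whom 1 and 2 have a given type. Printed: 1/2 = 50.0% against 2/6 = 33.3%. Per randomised participant: 1/80 = 1.25% against 2/80 = 2.5%.

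**Event-level rows (footnote 3).** These are also open to dilution. With 4 severe of 40 events in sham and 8 of 120 in active (assumed), they print 10.0% against 6.7%, while severe events per randomised participant are 4/80 = 0.05 and 8/80 = 0.10.

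**The case against.** The case for leaving the tables alone has several sound parts.

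- **The information needed is on the page.** The participant-level rows carry the count as well as the percentage, each arm column is headed with its N, and the first row is per participant randomised. In the 40 vs 60 example the reader would also see 4 and 6 severe participants under N = 80 in each arm. The listings give the severity of each event by participant and arm. A reader might infer that the tables conceal an excess of severe events; they do not. The defect is in the percentage alone.
- **The conditional base is stated.** Section 8.1 describes the measure as "participants with at least one AE by maximum severity", the row labels of Tables 61 and 65 restrict it to those with an event, and all four tables footnote the denominator. The SAP uses the same nested style for reasons for early termination and for missed visits.
- **No formal decision uses these percentages.** SAP Section 8 plans no safety test, and the pause rules (Protocol Section 10.9, SAP Section 11.2.2) work on counts.
- **A higher any-AE rate with active treatment is not established.** Protocol Section 4.3.5 cites headache in about 25% after rTMS but gives no sham figure. The sham delivers electrical stimulation to the scalp (Protocol Section 11.3), and sites ask every participant about headache and application-site pain (Protocol Appendix A). A reader might infer that active-arm severity percentages will be diluted; the documents show only that they could be.
- **Dilution by mild events does not extend to all four tables.** It cannot occur in Tables 63 and 67.

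All of this stands and lowers the weight of the point. It does not make the percentage a valid between-arm comparison. A nested breakdown is harmless when it lists reasons for stopping. In a by-arm harms table, where the row above and the companion tables use participants randomised, it is easily misread as a risk.

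**Conclusion.** The point holds as a minor reporting correction. In four by-arm safety tables the participant-level severity or type percentage depends on a post-randomisation event and does not estimate the risk in the arm. Under the assumed counts its effect ranges from none, when any-event rates are equal, through shrinkage and cancellation, to reversal (20.0% vs 16.0% printed, sham vs active, against 5.0% vs 10.0% per randomised participant). That the percentage is conditional follows from the footnotes and needs no assumption. The size and direction of any distortion rest on any-event rates by arm, which the documents do not give, and on 80 participants per arm.

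Tables 61 and 65 matter most, because no other summary table gives participants with Grade 3 events by arm. For serious events the gap is smaller: Table 63 gives participants with any SAE, and Table 64 the coded terms, per participant randomised. It would go too far to say that severe events are lost from the report or that the arms cannot be compared, since the count over N can be worked out from the same table.

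**What to change.** In Tables 61, 63, 65 and 67, change footnote 2 so that the participant-level severity and type rows are divided by the number randomised in the arm, the base already used in the first row. If the breakdown among participants with an event is wanted, keep it and print the randomised-base percentage beside it. Tables 61 and 65 are the priority. Adjust the two row labels there to match.

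Leave the event-level rows as they are, but label them as shares of events and not as between-arm risks.

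State the denominator in Section 8.1, and in 8.2 to 8.4 for the corresponding rows, and record the change in SAP Section 14. The cost is four footnotes and one denominator in the programs. No new data or model is needed, and the choice does not depend on results, so it can be made even though SAP version 2.0 contains updates made after database lock.
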